4.3 SAFETY FOLLOW-UP VISIT

Each subject should be followed for 30 (+7) days after his or her last dose of study drug (i.e., the "safety follow-up visit") until the final data cut-off to monitor for resolution or progression of AEs (see Section 6.3.6) and to document the occurrence of any new events regardless of whether the subject receives a new anticancer therapy or demonstrates disease progression within this timeframe. Subjects who withdraw consent should still be encouraged to complete the safety follow-up assessments, but these assessments cannot be mandated once consent is withdrawn. The Schedule of Assessments (Appendix 4, Appendix 5, and Appendix 6) describes the procedures

required for the safety follow-up.

4.4 TIME-TO-NEXT TREATMENT, DISEASE FOLLOW-UP, AND LONG-TERM FOLLOW-UP

Part 1

Subjects who discontinue study therapy and complete the 30-day safety follow-up will continue on study for follow-up of time-to-next treatment unless they withdraw consent for further follow-up (Appendix 4). Thus, all subjects receiving ≥1 dose of study drug will be followed during the immediate post-therapy period with long-term follow-up (LTFU) assessments unless the subject withdraws consent for such follow-up to be conducted. The date the subject is withdrawn from the study and the reason for discontinuation will be recorded and described on the appropriate eCRF.

Part 2 and Part 3

Subjects who have received ≥1 dose of study drug, discontinue study therapy, and complete the 30-day safety follow-up, will continue on study for follow-up of disease (for subjects who discontinued for reasons other than disease progression), time-to-next treatment, and survival unless they withdraw consent for further follow-up. All follow-up visits should occur approximately every 12 weeks (see Appendix 5 and Appendix 6 for detailed information):

- Disease follow-up: Subjects who discontinue for reasons other than disease
 progression will be followed for disease progression (via CT scans per
 investigator discretion), regardless of whether the subjects receive a new
 anticancer therapy. The time-to-next treatment information will also be collected.
 Subjects will then continue long-term follow-up (see #2 below).
- Long-term follow-up: Subjects who have disease progression, regardless of whether disease progression occurred during the study treatment period or the disease follow-up period, will be followed for time-to-next treatment and survival until death, lost to follow-up, or consent withdrawal.

The date the subject is withdrawn from the study and the reason for discontinuation will be recorded and described on the appropriate eCRF.

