2.1.1 Primary Objective

 To characterize the safety profile of acalabrutinib alone or in combination with rituximab in subjects with R/R FL

2.1.2 Secondary Objectives:

- To characterize the safety profile of acalabrutinib in combination with rituximab in subjects with previously untreated FL
- To characterize the PK profile of acalabrutinib alone or in combination with rituximab
- To evaluate the PD effects of acalabrutinib alone or in combination with rituximab
- To evaluate the activity of acalabrutinib alone or in combination with rituximab as measured by ORR, DOR, time-to-next treatment, and PFS

2.2 PART 2

Please note that enrollment for Part 2, Cohort 2 (R/R MZL: Acalabrutinib + Rituximab) of this study is closed.

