3 STUDY DESIGN

3.1 DESCRIPTION OF STUDY

This study will be conducted in 3 parts. Note: Text throughout the protocol applies to all parts of the study unless otherwise specified. At the time of Amendment 6, the sponsor made the decision to close Part 4 of the study (R/R DLBCL: Acalabrutinib + rituximab and lenalidomide).

Part 1

This part of the study is a Phase 1b, multicenter, open-label, randomized, parallel group study to be conducted at approximately 11 centers. Two cohorts will be

enrolled in parallel: The Relapsed/Refractory Cohort will include approximately 24 subjects with R/R FL, and the Treatment-Naive Cohort will include 12 subjects who have not previously been treated for FL. Note: At the time of Amendment 4, enrollment in Part 1 has been completed.

Arm 1: Acalabrutinib 100 mg by mouth (PO) BID administered approximately 12 hours apart (BID dosing=200 mg total daily dose) for 28 days

Arm 2: Acalabrutinib 100 mg PO BID administered approximately 12 hours apart (BID dosing=200 mg total daily dose) for 28 days, plus rituximab 375 mg/m² intravenous (IV) on Days 1, 8, 15, and 22 of Cycle 1 and Day 1 of Cycles 2 through 6

Treatment-Naive Cohort: A total of 12 subjects will receive the combination of acalabrutinib and rituximab: acalabrutinib 100 mg PO BID administered approximately 12 hours apart (BID dosing=200 mg total daily dose) for 28 days, plus rituximab 375 mg/m² IV on Days 1, 8, 15, and 22 of Cycle 1 and Day 1 of Cycles 2 through 6.

PK/PD testing will be performed in Cycle 1 and Cycle 2. Tumor assessments will be performed at 8- to 24-week intervals during the trial. Refer to Appendix 4 for a comprehensive list of study assessments and their timing.

Part 2

[figure not shown]
This part of the study is a Phase 2, multicenter, open-label, study to be conducted at approximately 38 centers. Up to 40 subjects with R/R MZL will be enrolled. Each cycle is 28 days. At the time of Amendment 6, the decision was made to close Cohort 2.

Cohort 1: Acalabrutinib 100 mg PO BID administered approximately 12 hours apart (BID dosing=200 mg total daily dose) for 28 days

Cohort 2: Acalabrutinib 100 mg PO BID administered approximately 12 hours apart (BID dosing=200 mg total daily dose) for 28 days, plus rituximab 375 mg/m² IV on Days 1, 8, 15, and 22 of Cycle 1 and Day 1 of Cycles 2 through 6.

The study schema for Part 2 of the study is presented in Figure 1.

Figure 1 Part 2 Study Schema

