3.8 WITHDRAWAL OF SUBJECTS FROM STUDY TREATMENT

Subjects may be withdrawn from study treatment for the following reasons:

- Progressive disease
- Completed treatment
- Start of alternative anticancer therapy
- Adverse event
- Pregnancy
- Investigator's decision
- Subject's withdrawal of consent from the study
- Decision by sponsor to terminate the study
- Subject lost to follow-up
- Death
- Other

Subjects who have received ≥1 dose of study drug and discontinue study therapy will continue to be followed on study for follow-up of safety (Section 4.3), disease, time-to-next therapy, and long-term follow-up (Section 4.4) unless they withdraw consent for further follow-up. The date the subject is withdrawn from study treatment or from the study and the reason for discontinuation will be recorded and described on the appropriate eCRF.

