Hematology ^j	Х	x ^{k.}	Х	Х	Х	Х	Х	Х	Х	Х	Х	Х	Х	
Serum chemistryl	Х	x k	Х	Х	Х	Х	Х	Х	Х	Х	Х	Х	Х	
Hepatitis serology ^m	Х													
HBV PCR ⁿ	Х					Х		Х	Х	Х	Х	Х	Х	Х
HCV PCR ⁿ	Х													
Urinalysis ^o	Х													
T/B/NK cell count ^p		χ ^k						Х		Х				
Serum Ig ^q		χk						Х		Х			Х	
Bone marrow (aspirate/biopsy) ^r	х							to cor		f bone mar phoma at l	row was invo	olved by		
Pharmacodynamics		X ^m	Xm			X ⁿ		X ⁿ					Х	
Pharmacokinetics ^u		Х	Х	Х	Х	Х						_		
Acalabrutinib dispensed		Х				Х		Х	Х	Х	Х	Х		
Rituximab administered ^v		Х	Х	Х	Х	Х		Х	Х					
Study drug compliance		Х	Х	Х	Х	Х	Х	Х	Х	Х	Х	Х		
Tumor assessment ^r	Х	Х	Х	Х	Х	Х	Х	Х	Х	Х	х	Х		
Concomitant medications	Х	Х	Х	Х	Х	Х	Х	Х	Х	Х	х	Х	Х	
Adverse eventsw		Х	Х	Х	Х	Х	х	Х	Х	Х	х	Х	Х	
Time-to-next treatment			1											Х

anti-HBc=hepatitis B core antibodies; anti-HBs=hepatitis B surface antibody; CR=complete remission; CT=computed tomography; ECOG=Eastern Cooperative Oncology Group, FL=follicular lymphoma; HBsAg=hepatitis B surface antigen; HBV=hepatitis B virus; HCV=hepatitis C virus; Ig=immunoglobulin; IVIG=intravenous immunoglobulin; LTFU=long-term follow-up; PCR=polymerase chain reaction; PE=physical examination; PET=positron-emission tomography; T/B/NK=T cell/B cell/natural killer.

- a. Screening tests should be performed within 21 days before the first administration of study drug, unless otherwise indicated.
- b. Treatment with acalabrutinib may be continued until disease progression or an unacceptable drug-related toxicity occurs as defined in the protocol. The end of the study is defined as the final data cut-off for the final analysis (Section 3.2).
- c. Study assessments (including clinical evaluations, laboratories, and CT) are required on Day 1 of Cycle 13 and every 3 cycles thereafter (i.e., Cycles 16, 19, etc.).
- d. Until the final data cut-off, a 30-day (+7 days) safety follow-up visit is required when subjects discontinue study drug.
- e. Subjects who discontinue study therapy will continue on study for long-term follow-up of time-to-next therapy for FL (every 8-12 weeks) unless they withdraw consent for further follow-up.
- f. The physical examination includes height (screening only) and weight, and examination of the skin, eyes, ears, nose, throat, lungs, heart, abdomen, extremities,

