- n. Subjects who are anti-HBc positive (or have a known history of HBV infection) should have PCR testing for HBV DNA performed during screening and monthly thereafter. Monthly monitoring should continue until 12 months after last dose of study drug. Any subject with a rising viral load (above lower limit of detection) should discontinue study drug(s) and have antiviral therapy instituted and a consultation with a physician with expertise in managing hepatitis B. If the HBV DNA PCR is needed during long-term follow-up, it can be performed at a local laboratory. Subjects with a known history of hepatitis C or who are hepatitis C antibody positive should be tested by quantitative PCR for HCV RNA during screening. Such subjects may be enrolled provided the quantitative PCR is negative (undetectable viral load). No further monitoring for HCV RNA during treatment is necessary if initial PCR results are negative.
- o. Urinalysis: pH, ketones, specific gravity, bilirubin, protein, blood, and glucose.
- p. T/B/NK cell count (i.e., CD3+, CD4+, CD8+, CD19+, CD16+/56+).
- q. Serum immunoglobulin: IgG, IgM, IgA.
- r A pretreatment CT scan with contrast (unless contraindicated) is required of the chest, abdomen, and pelvis and any other disease sites (e.g., neck) within 30 days before the first dose of study drug. A pretreatment PET/CT scan within 60 days before the first dose of study drug. During treatment, CT scans will be performed for tumor assessments on Day 1 of Cycle 3 (±7 days), Cycle 5 (±7 days), Cycle 7 (±7 days); and then every 3 cycles (12 weeks, ±7 days) thereafter (i.e., Cycles 10, 13, 16, etc.) up to 2 years then every 6 cycles (24 weeks) or more frequently at the investigator's discretion. Bone marrow (if bone marrow was involved by lymphoma at baseline) and PET/CT are required to confirm CR per clinical guidelines (see Section 4.2). When possible, extra bone marrow tissue may be used for pharmacodynamic evaluation. At all other visits, tumor assessments will be performed by physical examination and laboratory results.
- s. Pharmacodynamic samples are drawn predose and 4 hours (±10 minutes) postdose on the days indicated. Timepoints are relative to the morning dose.
- t. Pharmacodynamic samples are drawn predose on the days indicated.
- u. Pharmacokinetic samples are drawn per Table 4.
- Rituximab 375 mg/m² IV on Days 1, 8, 15 and 22 of Cycle 1 and Day 1 of Cycles 2 through 6.

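### Part 1 schedules no disease follow-up after treatment stops, contrary to Protocol Section 3.8, so progression before the next therapy can be missed in PFS and DOR

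*Protocol*

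**What the plan says.** **General rule.** Section 3.8 covers every subject who has had at least one dose and then stops treatment. Such subjects "will continue to be followed on study for follow-up of safety (Section 4.3), disease, time-to-next therapy, and long-term follow-up (Section 4.4"). Withdrawal of consent is the only exception, and the section names no part. Section 3.1 sets the scope of such text: "Note: Text throughout the protocol applies to" all parts unless stated otherwise.

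**Part 1.** Section 4.4 says that Part 1 subjects who stop therapy and "complete the 30-day safety follow-up will continue on study for follow-up of time-to-next treatment unless they withdraw consent". Appendix 4 agrees. Its footnote e reads "Subjects who discontinue study therapy will continue on study for long-term follow-up of time-to-next therapy for FL (every 8-12 weeks"). The long-term follow-up column holds only HBV PCR and time-to-next treatment. The tumor assessment row ends with the column for Cycle 13 onward, and there is no disease follow-up column. Footnote r places imaging in the treatment period: "During treatment, CT scans will be performed for tumor assessments on Day 1 of Cycle 3 (±7 days"), and so on. Section 4.1.22 does the same.

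**Parts 2 and 3.** Under Section 4.4, subjects in these parts who stop therapy and "complete the 30-day safety follow-up, will continue on study for follow-up of disease (for subjects who discontinued for reasons other than disease progression"). Appendices 5 and 6 each have a disease follow-up column that includes tumor assessment.

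**Endpoints.** Section 2.1.2 makes activity a Part 1 secondary objective, "as measured by ORR, DOR, time-to-next treatment, and PFS". Section 5.5.4 defines PFS and DOR by progression or death from any cause. Section 5.4 censors subjects without an event at the last tumor assessment and before alternative anticancer therapy. The supplied SAP covers Parts 2 and 3 only.

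**The concern.** Section 3.8 refers to Section 4.4 for the detail, but for Part 1 Section 4.4 contains no disease follow-up. No other section supplies it.

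The consequence follows from the censoring rule. A Part 1 subject who stops for an adverse event or by investigator decision has no further scheduled tumor assessment, so PFS and DOR normally end at the last on-treatment assessment. The site still makes contact every 8 to 12 weeks, but the question scheduled is whether a new therapy has begun, not whether the disease has progressed. If the risk of progression changes when treatment stops, this censoring is informative, and the Kaplan-Meier curves mainly describe the time on drug.

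Capture may also be uneven. A death after stopping may reach the database through study-exit recording, while a progression over the same interval has no planned route. Later deaths would then count as events and later progressions would not.

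**Working it through.** **1. Text check.**

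| Item | Section 3.8 (all parts) | Part 1 (4.4, App. 4) | Parts 2 and 3 (4.4, App. 5, 6) |
|---|---|---|---|
| Disease follow-up after stop | yes | none | yes |
| Tumor assessment after stop | by reference to 4.4 | none scheduled | yes |
| Time to next treatment | yes | every 8 to 12 weeks | about every 12 weeks |
| Survival contact | by reference to 4.4 | none scheduled | yes |
| Death as study-exit reason (3.9) | yes | yes; exit date and reason on eCRF | yes |

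**2. Figures in the plan.** The documents give none for this point. The only Part 1 statistical figures are the chances of seeing at least one adverse event (Section 5.2). They reproduce from 1 − (1 − p)^n: 84.2% and 97.8% for n = 36, and 46.0% and 71.8% for n = 12. They do not bear on follow-up.

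**3. Size of the effect: assumptions.** The documents give no Part 1 stopping rate, post-stop hazard or time to next therapy, so all of these are assumed.
- On-treatment PFS hazard l = ln 2/24 = 0.0289 per month, a 24-month median.
- Share stopping before progression s/(s + l) = 15% or 30%, so s = 0.0051 or 0.0124 per month. That is 0.15 × 36 = 5.4 or 0.30 × 36 = 10.8 of 36 subjects.
- Post-stop hazard k·l, with k = 1, 1.5, 2 or 3.
- Start of next therapy after stop at rate n = ln 2/6 = 0.1155 per month, a 6-month median.

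**4. Censoring at stop, as scheduled.** Only on-treatment subjects are at risk, so the hazard is l and the median is 24.0 months whatever k is.

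**5. Disease follow-up until next therapy.** Section 5.4 censors before alternative therapy, so follow-up can add progressions only between stop and next therapy. With a = l + s and b = k·l + n:
- on treatment and at risk: A(t) = exp(−a·t)
- off treatment, at risk, no new therapy: B(t) = s·[exp(−b·t) − exp(−a·t)]/(a − b)
- hazard estimated by Kaplan-Meier: l·(A + k·B)/(A + B)
- the median is the time at which the integrated hazard equals ln 2.

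| k | 15% stop | 30% stop |
|---|---|---|
| 1 | 24.00 | 24.00 |
| 1.5 | 23.68 | 23.25 |
| 2 | 23.41 | 22.65 |
| 3 | 22.99 | 21.73 |

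Against 24.0, the difference for k = 1.5 to 3 is 0.3 to 1.0 months (15%) or about 0.8 to 2.3 months (30%).

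**6. Sensitivity to time to next therapy.** Over the same grid, a 3-month median gives differences of 0.2 to 1.6 months, and a 12-month median 0.4 to 2.8. With no censoring at next therapy, S(t) = exp(−a·t) + s·exp(−k·l·t)·[1 − exp(−(a − k·l)·t)]/(a − k·l). The medians are then 23.4 to 22.3 (15%) and 22.7 to 20.5 (30%). That is an upper limit the protocol's own censoring rule excludes.

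**7. Against sampling error.** With 10 events in a 12-subject arm (assumed), the exact exponential 95% interval around 24 months runs from 2·10·24/34.17 = 14 to 2·10·24/9.59 = 50 months.

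**The case against.** Several stronger readings are tempting, and the documents do not support them.

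- **Deaths after stopping go unrecorded.** A reader might infer this from the missing survival row in Appendix 4. But Part 1 subjects remain on study, Section 3.9 lists death as a reason for study exit, and Section 4.4 (Part 1) puts exit date and reason on the eCRF. Section 6.3.5 also has deaths from progression entered in the data capture system. The survival row is absent because OS is not a Part 1 endpoint.
- **Time-to-next treatment is compromised too.** It is exactly what the Part 1 contact collects, and its censoring at death can use the exit record. No defect is shown.
- **An early stopper loses over five years of information.** The Part 1 cut is about 71 months after the last subject's first dose (Section 3.2), but censoring before alternative therapy leaves only the interval up to that therapy.
- **Part 1 and Part 3 PFS are made incomparable.** No such comparison is planned, and Section 4.4 leaves the Parts 2 and 3 follow-up scans to investigator discretion, although Appendix 6 footnote e is firmer.

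The best remaining defense is that Section 4.4 is the specific text and narrows a general pointer in Section 3.8. That softens the contradiction but leaves a stated promise with nothing behind it for Part 1. Two further points count in part. Progression evident at the 30-day physical examination could be imaged under Section 4.2, though no scan is scheduled. A Part 1 SAP could refine censoring, but it could not supply assessments the protocol does not schedule.

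**Conclusion.** The inconsistency is real. Its consequence is confined to progression between treatment stop and next therapy in Part 1 PFS and DOR. Under the assumptions above, the effect is about 0.3 to 2.3 months on a 24-month median, well inside the sampling error of a 12-subject arm. Direction and size both rest on an assumed rise in hazard after stopping. With no change there is no bias, only lost information, so the documents do not establish that PFS and DOR are flattered. The endpoints are descriptive and the Part 1 primary objective, safety, is untouched. The point should be fixed because the remedy is cheap, not because the study's conclusions depend on it.

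**What to change.** 1. Reconcile Section 4.4 (Part 1) and Appendix 4 with Section 3.8.
2. At the existing 8- to 12-week long-term follow-up contact, record progression status and date from routine-care evaluation, and the date of last disease evaluation, up to the start of next therapy. Confirm vital status at the same contact so that deaths and progressions are captured on the same footing.
3. If the Part 1 database is not yet locked, retrieve these items from medical records for subjects already off treatment and use them in PFS and DOR. The documents do not show whether that lock is still ahead.
4. In any case, report how many Part 1 subjects were censored at a treatment stop without progression, by group.

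The cost is amendment wording and a few eCRF fields at a contact already made; no scan is added. Off-treatment progression dates will be less regular than scheduled ones, and PFS and DOR may come out slightly shorter.

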4.5 MISSED EVALUATIONS

Missed evaluations should be rescheduled and performed as close to the original scheduled date as possible. An exception is made when rescheduling becomes, in the

investigator's opinion, medically unnecessary or unsafe because it is too close in time to the next scheduled evaluation. In that case, the missed evaluation should be abandoned.

5 STATISTICAL METHODS OF ANALYSIS

5.1 GENERAL CONSIDERATIONS

Descriptive statistics (including means, standard deviations, and medians for continuous variables and proportions for discrete variables) will be used to summarize data as appropriate. All analyses will be done by indication, treatment, and overall.

5.2 SAMPLE SIZE CONSIDERATIONS

Part 1

This study will assess acalabrutinib safety, PK, PD, and antitumor activity when administered alone or in combination with rituximab. A total of 24 subjects (12 each arm) in the Relapsed/Refractory Cohort will be equally randomized into 1 of 2 treatment arms (monotherapy and combination therapy). Twelve subjects will be enrolled to the Treatment-naive Cohort receiving the combination therapy. The study is not formally designed to compare these regimens but rather to obtain descriptive information that can be used in support of further acalabrutinib development.

The primary objective of this study is to determine the safety as such:

- With a total sample size of 36, the probability of observing one or more instances
 of an AE with a background rate of 5% and 10% is 84% and 98%, respectively.
- For each treatment arm (n=12 each), the probability of observing one or more instances of an AE with a background rate of 5% and 10% is 46% and 72%, respectively.
- This provides reasonable assurance for generating preliminary safety data for this Phase 1b, proof-of-concept study.

Part 2

Part 2 will enroll up to 40 subjects in Cohort 1. The primary objective is to characterize the activity of acalabrutinib alone in subjects with R/R MZL as measured by the ORR. Up to 40 subjects in treatment Cohort 1 will provide data for an initial assessment of safety and efficacy of acalabrutinib treatment. Sample size is not based on statistical power consideration.

Part 3

A total of approximately 26 to 32 subjects are to be enrolled in Part 3. This sample size will provide adequate data for an initial assessment of safety and efficacy of acalabrutinib treatment in combination with lenalidomide and rituximab. This sample size is not based on statistical power consideration.

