	Use of proton-pump inhibitors, H2 receptor antagonists, or antacids while taking acalabrutinib capsules has the potential to decrease acalabrutinib exposure. If treatment with a gastric acid-reducing agent is required, consider using a H2-receptor antagonist (2 hours after acalabrutinib capsules) or antacid (2 hours before or 2 hours after acalabrutinib capsules). Avoid coadministration of proton-pump inhibitors with acalabrutinib capsules. Acalabrutinib maleate tablets can be taken without regards to acid-reducing agents (such as antacids, H2-receptor antagonists, or proton-pump inhibitors).
	Lenalidomide
	Subjects who are concurrently receiving digoxin should have periodic monitoring of digoxin plasma levels is due to increased C_{max} and AUC_{inf} of digoxin with concomitant lenalidomide therapy. Moreover, subjects taking concomitant therapies such as erythropoietin-stimulating agents or estrogen-containing therapies, along with lenalidomide, may have an increased risk of venous thromboembolic events per package insert.
	Rituximab
	The only drug-drug interaction with rituximab listed in the Rituxan/MabThera package insert is renal toxicity when used in combination with cisplatin.
Statistics:	Descriptive statistics (including means, standard deviations, and medians for continuous variables and proportions for discrete variables) will be used to summarize data as appropriate. All analyses will be done by indication, treatment, and overall.

Part 1

This study will assess acalabrutinib safety, PK, PD, and antitumor activity when administered alone or in combination with rituximab. The primary objective of this study is to determine the safety as such:

- With a total sample size of 36, the probability of observing one or more instances of an AE with a background rate of 5% and 10% is 84% and 98%, respectively.
- For each treatment arm (n=12 each), the probability of observing one or more instances of an AE with a background rate of 5% and 10% is 46% and 72%, respectively.

Part 2

The primary objective is to characterize the activity of acalabrutinib alone in subjects with R/R MZL as measured by the ORR. Up to 40 subjects in treatment Cohort 1 will provide data for an initial assessment of safety and efficacy of acalabrutinib treatment. Sample size is not based on statistical power consideration.

Part 3

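### The 84% and 98% detection probabilities given under the Part 1 primary safety objective are for all 36 subjects; for the 24 R/R FL subjects that the objective covers, they are 71% and 92%

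*Protocol*

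**What the plan says.** Protocol Section 2.1.1 gives the Part 1 primary objective as "To characterize the safety profile of acalabrutinib alone or in combination with rituximab in subjects with R/R FL". Section 2.1.2 lists as a secondary objective "To characterize the safety profile of acalabrutinib in combination with rituximab in subjects with previously untreated FL".

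Section 5.2 sets the numbers: "A total of 24 subjects (12 each arm) in the Relapsed/Refractory Cohort will be equally randomized into 1 of 2 treatment arms", and "Twelve subjects will be enrolled to the Treatment-naive Cohort receiving the combination therapy". It then introduces the detection probabilities with "The primary objective of this study is to determine the safety as such". The first bullet reads "With a total sample size of 36, the probability of observing one or more instances" and continues "of an AE with a background rate of 5% and 10% is 84% and 98%, respectively". A second bullet gives 46% and 72% for each arm of 12. A third, following both, concludes that there is reasonable assurance of obtaining preliminary safety data. The synopsis (Statistics, Part 1) repeats the lead-in and the first two bullets, again starting from "With a total sample size of 36, the probability of observing one or more instances of an AE".

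No probability is given for 24 subjects.

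**The concern.** The lead-in ties the probabilities to the primary objective, yet one third of the 36 subjects (12 of 36) belong to a cohort that this objective does not cover. The treatment-naive cohort has its own eligibility definition in Section 3.4.1, and Section 3.3 describes Part 1 as designed around R/R follicular lymphoma. A reader who takes 84% and 98% as what the design offers for its primary question has figures that are too favourable.

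What is at stake is interpretation. Section 3.2 provides for a separate clinical study report on Part 1. If that report carries the Section 5.2 rationale over unchanged, the absence of an event in the R/R cohort could be given more weight than that cohort supports. The SAP supplied covers Parts 2 and 3 only (SAP Section 1), so it neither repeats nor corrects the figure.

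**Working it through.** **Inputs.** All are from Protocol Section 5.2, except the objective's population, which is from Section 2.1.1.

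- R/R cohort: 24 planned, 12 per arm.
- Treatment-naive cohort: 12 planned. Part 1 total: 24 + 12 = 36.
- Adverse event rates: 5% and 10%.
- Primary objective: R/R follicular lymphoma only.

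**Formula.** With n subjects and a common event rate p, the probability of at least one event is 1 − (1 − p)^n, and the chance of seeing none is (1 − p)^n.

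**Step 1: reproduce the plan's figures.**

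- n = 36: 1 − 0.95^36 = 0.842 and 1 − 0.90^36 = 0.977. The protocol states 84% and 98%.
- n = 12: 1 − 0.95^12 = 0.460 and 1 − 0.90^12 = 0.718. The protocol states 46% and 72%.

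All four stated figures are correct for the n that they name.

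**Step 2: apply the same formula to the population of the primary objective.**

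- n = 24: 1 − 0.95^24 = 0.708 and 1 − 0.90^24 = 0.920.

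| Subjects | At least one event, 5% rate | At least one event, 10% rate | No event seen, 5% rate |
|---|---|---|---|
| 36, all of Part 1 | 84% | 98% | 16% |
| 24, R/R cohort | 71% | 92% | 29% |
| 12, one arm | 46% | 72% | 54% |

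The figures for the primary population are 13 points lower at a 5% rate (84 − 71) and 6 points lower at a 10% rate (98 − 92).

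**Step 3: the same gap as an event rate.** The lowest rate that would be seen at least once with 95% probability is 1 − 0.05^(1/n). At n = 36 this is 8.0%; at n = 24 it is 11.7%.

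**The case against.** Several points on the other side stand.

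- **The total is openly labelled.** Section 5.2 says that 36 is the total and sets out the 24 and the 12 just above. It nowhere says that 36 is the size of the R/R cohort. A reader might infer a calculation error; the documents do not support that, since every stated figure reproduces.
- **Other design properties are stated.** A reader might infer that 84% and 98% are all that the protocol offers and that its claim of reasonable assurance rests on them alone. That is not so. The 12-subject figures apply directly to each R/R arm and are more cautious than 71% and 92%. They already show that a 5% event would be missed 54% of the time in one arm, and the reasonable-assurance bullet follows both sets.
- **A pooled summary is planned.** Section 5.1 calls for analyses by indication, by treatment and overall, and Section 5.3 runs safety analyses on all treated subjects. The 36-subject figure therefore has a use.
- **The 24 also mixes regimens.** No regimen has 36 subjects, but the R/R cohort is itself 12 on monotherapy and 12 on the combination, so 71% and 92% assume one event rate across both arms.
- **Nothing depends on the figure.** Section 5.2 describes Part 1 as descriptive and not designed to compare regimens. No hypothesis test, stopping rule or sample-size derivation uses these probabilities, and enrolment was complete by Amendment 4.

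These points limit the weight of the concern without removing it. A pooled figure may be reported, but it should not stand without qualification as the lead figure under an objective restricted to R/R disease, when the figure for that population is absent.

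**Conclusion.** The protocol is internally inconsistent: Section 2.1.1 confines the Part 1 primary safety objective to R/R follicular lymphoma, while Section 5.2 and the synopsis support it with probabilities for a total that includes the treatment-naive cohort. For the 24 planned R/R subjects the figures are 71% and 92%, and a 5% event would go unseen with probability 29% rather than 16%.

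This assumes that all 24 are treated and that the two R/R arms share a common event rate. The actual number may differ: the synopsis and Section 3.1 give the cohort as approximately 24, and Section 3.4.7 allows replacement of subjects who do not complete Cycle 2.

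A reader might go further and infer that Part 1 was too small or that its safety conclusions are compromised. The documents do not support this. Part 1 has no power target, it aims only at preliminary descriptive data, and no passage uses these probabilities to interpret an event that was not observed. The severity is minor.

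**What to change.** In Section 5.2 and the synopsis:

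1. Give the figure for the primary objective as that of the 24-subject Relapsed/Refractory Cohort: 71% for a 5% event rate and 92% for a 10% rate, noting that it assumes a common rate across the two arms.
2. Keep the 12-subject bullet as it is.
3. Keep the 36-subject figures, labelled as all Part 1 subjects pooled across cohorts and regimens.

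If the Part 1 study report discusses events that were not observed, it should recompute the probability from the number of R/R subjects actually treated, not from the planned 24. If the protocol is not amended again, the correction can be made in that report.

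The cost is about two sentences in each place and a less favourable stated figure. Enrolment and analyses do not change.
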